14.2. Sample Size Justification

Phase I of this study was not powered to test non-inferiority of O1D relative to P1 with respect to the primary endpoints. However, data collected during Phase I of the study will be used to power Phase II to test for superiority of the O1D relative to P1 with respect to *Overall comfort*,

Clinical Study Protocol

Johnson & Johnson Vision Care, Inc.

Comfort at the End of the Day and Dryness at the End of the Day. Based on these results from testing for non-inferiority for each primary endpoint from the interim analysis (Phase I analysis), the sample size will be calculated to test all three primary hypotheses for superiority with at least 80% power. This will be calculated using an approximation of the power of an F-test derived from the non-centrality parameter calculated from the observed F-statistic from the generalized linear model described in Section 14.5 for Phase I.⁹ If the sample size calculation for Phase II exceeds 300 then the Sponsor reserves the right to terminate the study. Alpha will be adjusted as described in Section 14.4. Complete details of the sample size calculation for Phase II are described in Section 14.5.

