14.4. Level of Statistical Significance

All type I error adjustments utilized in this study were calculated using a Bonferroni¹⁰ correction.

Primary hypotheses in Phase I will be tested using a familywise type I error rate of 5%; each hypothesis will be tested using an individual type I error rate of 1.67%.

Hypotheses in Phase II will be tested using the following strategy:

Primary hypotheses will be tested using a familywise type I error rate of 5%; each hypothesis will be tested using an individual type I error rate of 1.67%. All primary hypotheses must be met in order to test any secondary hypotheses. Secondary hypotheses were grouped according to item semantic similarities. Each secondary hypothesis group will be tested using an overall type I error rate of 5% and in a sequential order. Each preceding secondary hypothesis group must be fully met in order to continue testing the remaining secondary hypotheses. Exploratory hypotheses will only be tested if all primary and secondary group 2 hypotheses are met.

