$$\begin{aligned}H_0: OR &\leq 0.67 \\H_a: OR &> 0.67\end{aligned}$$

Where, the OR represents the odds of having a more positive experience (Excellent or Very Good) while wearing O1D compared to P1. Non-inferiority of O1D relative to P1 will be concluded if the lower limit of the 97.5% CI is above 0.67 (using 10% as non-inferiority margin and assuming a reference proportion of 0.5).

Clinical Study Protocol

Johnson & Johnson Vision Care, Inc.

Sample size Estimation for Phase II

If non-inferiority is demonstrated for the primary endpoints, the sample size required to test superiority for each primary endpoint will be estimated. The odds ratio and the cumulative log-odds from the model described above for each endpoint will be used to create a new dataset with the same structure and design as Phase I. This new dataset will then be analyzed using the same model. The statistical power of each endpoint will be calculated using the F-statistics as $\text{Power} = P(F[F_{\text{crit}}, v, ncp] > F_{\text{crit}})$; where F_{crit} is the critical value of the central F distribution ($F_{\text{crit}} = F_{\text{numdf}, \text{dmdf}, 0, \alpha}$) under H_0 (H_0 : centrality param = 0), v is the magnitude of the departure from H_0 and ncp is the non-centrality parameter (Stroup).⁹

Phase II

Overall comfort, Comfort at the end of the day, and Dryness at the end of the day

Subjective responses to each primary endpoint will be grouped as: $aval=1$ is a subject responds' 'Excellent' or 'Very Good', $aval=2$ is a subject responds' 'Good' and $aval=3$ if a subject responds' 'Fair' or 'Poor'. $Aval$ will be analyzed separately for each primary endpoint using a generalized linear mixed model with a multinomial distribution and the cumulative logit as the link function. In each model, sequence of lens wear, period and lens type will be included as fixed effects. Site and subject nested within site will be included as a random effect. Errors between measurements within the same subject across study periods will be modeled using an unstructured covariance (UN) structure. Comparisons between O1D and P1 will be carried out using 1-sided 97.5% confidence intervals (CIs) constructed for the odds ratio (O1D over P1). Superiority of O1D relative to P1 will be concluded if the lower limit of the 97.5% CI is above 1.

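### Replacing the equal Bonferroni split over the three primaries with Holm would raise the chance of meeting all three by about 9 to 19 points at the same familywise error, once Sections 14.4 and 14.5 agree on the test level

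*Combined protocol and SAP*

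**What the plan says.** - Section 14.4, method: "All type I error adjustments utilized in this study were calculated using a Bonferroni" correction. In both phases the primaries share a 5% familywise rate, 1.67% each. The text does not say whether the 5% is one-sided or two-sided.
- Section 14.4, level and gate (Phase II): "each hypothesis will be tested using an individual type I error rate of 1.67%. All primary hypotheses must be met" before any secondary is tested.
- Section 14.2, sizing: "the sample size will be calculated to test all three primary hypotheses for superiority with at least 80% power", with alpha adjusted as in 14.4. If the calculation gives more than 300 subjects, the sponsor keeps the right to terminate.
- Section 14.5, link from Phase I to Phase II: "If non-inferiority is demonstrated for the primary endpoints, the sample size required to test superiority for each primary endpoint will be estimated". Power is then worked out one endpoint at a time.
- Section 14.8 describes the 80% as the power to achieve all the primary hypotheses, which reads as joint power.
- Section 14.5, Phase II success rule: "Comparisons between O1D and P1 will be carried out using 1-sided 97.5% confidence intervals (CIs) constructed for the odds ratio", with superiority concluded when the lower limit exceeds 1. Phase I non-inferiority also uses a 97.5% limit, against 0.67.

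**The concern.** The plan wants all three primaries: they open the secondaries, and Phase II is sized to reach them. Under an equal Bonferroni split even the weakest endpoint must clear one third of alpha. Holm asks that only of the strongest. After one rejection the next endpoint is tested at alpha/2, and after two the last is tested at the full alpha. Whatever Bonferroni rejects, Holm rejects too, and the familywise error is still controlled under any dependence between the three ratings.

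At stake are a lower chance of meeting all three for a given number of subjects and, because the 14.4 level feeds the sizing step, a larger calculated Phase II. A larger figure brings the study closer to the 300 ceiling, where it may be stopped for size.

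**Working it through.** **Plan's own figure.** 5% / 3 = 1.67%, and 3 × 1.67% = 5%. It reproduces. The documents give no Phase II sample size, effect size or achieved power, so no power figure can be checked.

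**Inputs from the documents.** Three primaries, familywise 5% (14.4), 80% power (14.2, 14.8), 1-sided 97.5% intervals (14.5).

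**Assumed.** Equal effects on the three endpoints and a common correlation r of 0.3 to 0.85. The familywise 5% is run both as 5% one-sided and as 5% two-sided (2.5% one-sided).

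**Method.** Three normal test statistics with common mean m and correlation r, 1,000,000 draws per setting, one-sided p-values. All three are met when:

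- Bonferroni: largest p ≤ α/3.
- Holm: smallest p ≤ α/3, middle p ≤ α/2, largest p ≤ α.
- Section 14.5 rule: largest p ≤ 2.5%.

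**A. 80% power per endpoint at the Bonferroni level.** m = z(1−α/3) + 0.842. Probability of meeting all three (%):

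| 5% taken as | r | Bonferroni | Holm | Gain (points) | 14.5 rule |
|---|---|---|---|---|---|
| one-sided | 0.3 | 57.1 | 76.0 | 18.9 | 64.8 |
| one-sided | 0.5 | 61.1 | 77.9 | 16.8 | 68.2 |
| one-sided | 0.7 | 65.9 | 80.3 | 14.4 | 72.2 |
| one-sided | 0.85 | 70.3 | 82.2 | 11.9 | 76.0 |
| two-sided | 0.3 | 56.9 | 74.5 | 17.6 | 75.6 |
| two-sided | 0.5 | 61.2 | 76.7 | 15.5 | 78.0 |
| two-sided | 0.7 | 65.8 | 79.2 | 13.4 | 80.9 |
| two-sided | 0.85 | 70.2 | 81.5 | 11.3 | 83.7 |

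Holm against Bonferroni: about 11 to 19 points.

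**B. 80% joint power under Bonferroni.** m is chosen so that Bonferroni meets all three with probability 80%. At r = 0.3, 0.5, 0.7 and 0.85:

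- 5% one-sided: Holm reaches 91.5, 90.9, 90.2 and 89.2%, a gain of 11.5 to 9.2 points.
- 5% two-sided: Holm reaches 90.7, 90.1, 89.5 and 88.7%, a gain of 10.7 to 8.7 points.

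Since m grows with the square root of N, the sample-size ratio for 80% joint power is (m under Holm / m under Bonferroni)². It is 0.76 to 0.81, so Holm needs about 19% to 24% fewer subjects.

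**C. Holm against the rule in Section 14.5.** From table A:

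- 5% two-sided: 74.5 − 75.6 = −1.1 at r = 0.3 and 81.5 − 83.7 = −2.2 at r = 0.85. Here 2.5% one-sided is already the full alpha on every endpoint, so 14.5 loses nothing and Holm is slightly lower.
- 5% one-sided: 76.0 − 64.8 = 11.2 at r = 0.3 and 82.2 − 76.0 = 6.2 at r = 0.85. Holm gains about 6 to 11 points. On the joint-80% basis the 14.5 rule reaches 85.0 to 84.5%, so the gain is smaller, about 5 to 7 points.

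The 14.5 levels sum to 3 × 2.5% = 7.5%. A Bonferroni-consistent one-sided bound would be 98.33% (5% one-sided) or 99.17% (5% two-sided).

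**The case against.** The strongest objection is that Section 14.5, not 14.4, decides success. Its 97.5% bounds use 2.5% per endpoint, so a loss measured at 1.67% may never arise in the final test. This stands. A reader might infer that the loss holds whatever interval level is finally chosen, but part C shows that it does not. What remains is the rule written in 14.4, the sizing under 14.2 that uses it, and the final test if 14.5 is brought into line with 14.4.

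A second objection is that the size rests on assumptions. That also stands. With 95% power on each endpoint the gain falls to about 4 to 9 points for correlations of 0 to 0.9.

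A reader might also infer that no split is needed, because an all-must-be-met rule keeps its error at alpha when each test runs at alpha. That is true of the gate alone. The documents do not say that a single met primary cannot be claimed, so adjusting for such claims is legitimate. Running a full-alpha gate beside Holm claims would also give two meanings to a hypothesis being met. With p = 0.04 on all three and alpha 0.05, the gate would open although Holm rejects nothing, since 0.04 exceeds 0.0167. Familywise control would then no longer follow from Holm's theorem alone. Using Holm for the gate as well costs only 0.4 to 2.7 points of all-three power.

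**Conclusion.** The point holds as a matter of efficiency. At the level written in Section 14.4, Bonferroni gives up about 11 to 19 points of all-three power if 80% is per endpoint, or about 9 to 12 points if it is joint. Both ranges assume correlations of 0.3 to 0.85 and equal effects, neither of which the documents supply. The direction needs no such assumption, because Holm never rejects less at the same familywise error.

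Two further inferences are not supported. Bonferroni is valid and conservative, so the split does not inflate type I error. The separate conflict between 1.67% in 14.4 and 2.5% in 14.5 must be reconciled before any loss can be attached to the final test. Nor does a larger calculated sample size force a stop: above 300 the sponsor may terminate but is not bound to (14.2, 14.8).

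**What to change.** 1. In 14.4, state whether the familywise alpha is one-sided or two-sided.
2. In 14.4, replace Bonferroni with Holm for the primaries: smallest p at alpha/3, next at alpha/2, last at alpha, stopping at the first failure. Require all three Holm rejections to open the secondaries. Use this one definition of met, with no separate full-alpha gate.
3. In 14.5, set the one-sided interval levels to the Holm steps: 98.33%, 97.5% and 95% for 5% one-sided, or 99.17%, 98.75% and 97.5% for 5% two-sided.
4. In 14.2 and 14.5, size Phase II on the probability of meeting all three under Holm, and state the endpoint correlation used.

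The cost is a few lines in three sections, plus a joint power calculation in place of three separate ones. The downside is that Holm has no single simultaneous confidence level, so the three intervals should be reported at their step levels and labelled as such.

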14.5. Primary Analysis

Phase I (Interim Analysis)

Overall comfort, Comfort at the end of the day, and Dryness at the end of the day

Clinical Study Protocol

Johnson & Johnson Vision Care, Inc.

Subjective responses to each primary endpoint will be grouped as: $aval=1$ is a subject responds' 'Excellent' or 'Very Good', $aval=2$ is a subject responds' 'Good' and $aval=3$ if a subject responds' 'Fair' or 'Poor'. $aval$ will be analyzed separately for each primary endpoint using a generalized linear model with a multinomial distribution and the general logit as the link function. In each model, sequence of lens wear, period, lens type and site id will be included as fixed effects. Prior to fitting the final models for the primary endpoints, allocation of subjects' completion between sites will be evaluated. If a difference of more than 30% is observed between sites, a likelihood ratio test for homogeneous variance will be conducted using a generalized linear mixed model with a multinomial distribution and the general logit as the link function. Comparisons between O1D and P1 will be carried out under the final model using 1-sided 97.5% confidence intervals (CIs) constructed for the odds ratio (O1D over P1).

The Model:

Let $aval_{ijkl} = (aval1_{ijkl}, aval2_{ijkl}, aval3_{ijkl})$ denote the rating for l^{th} subject at the m^{th} site assigned to the k^{th} sequence for the i^{th} study lens during the j^{th} study period ($i=1, 2$; $j=1, 2$; $k=1, 2$; $l=1, \dots, n_m$; $m=1, \dots, 10$). Possible values of $aval_{ijkl}$ are $aval_{ijkl}=1$ if a subject responds: 'Excellent' or 'Very Good', $aval_{ijkl}=2$ if a subject responds: 'Good' and $aval_{ijkl}=3$ if a subject responds: 'Fair' or 'Poor'. The Likelihood will be constructed as follows:

$$\begin{aligned}aval_{ijkl} &\sim \text{Multinomial}(p1_{ijkl}, p2_{ijkl}, p3_{ijkl}) \\p1_{ijkl} &= aval1_{ijkl} \\p2_{ijkl} &= aval2_{ijkl} - aval1_{ijkl} \\p3_{ijkl} &= 1 - \sum_{X=1,2} pX_{ijkl}\end{aligned}$$

$$\text{Logit}(avalX_{ijkl}) = \beta_0 + \beta_1 * sequence_k + \beta_2 * period_j + \beta_3 * lens_{i[j,k]} + \beta_4 * Site_m$$

Where, β_0 is the intercept for $X=1, 2, 3$; $sequence_k=1$ if O1D/P1 and $sequence_k=0$ if P1/O1D; $period_j=1$ if first period and $period_j=0$ if second period; $lens_{i[j,k]}=1$ if O1D and $lens_{i[j,k]}=0$ if P1.

Hypothesis Testing

Hypothesis testing will be conducted separately for each primary endpoint as follows:

$$\begin{aligned}H_0: OR &\leq 0.67 \\H_a: OR &> 0.67\end{aligned}$$

Where, the OR represents the odds of having a more positive experience (Excellent or Very Good) while wearing O1D compared to P1. Non-inferiority of O1D relative to P1 will be concluded if the lower limit of the 97.5% CI is above 0.67 (using 10% as non-inferiority margin and assuming a reference proportion of 0.5).

Clinical Study Protocol

Johnson & Johnson Vision Care, Inc.

Sample size Estimation for Phase II

If non-inferiority is demonstrated for the primary endpoints, the sample size required to test superiority for each primary endpoint will be estimated. The odds ratio and the cumulative log-odds from the model described above for each endpoint will be used to create a new dataset with the same structure and design as Phase I. This new dataset will then be analyzed using the same model. The statistical power of each endpoint will be calculated using the F-statistics as $\text{Power} = P(F[F_{\text{crit}}, v, ncp] > F_{\text{crit}})$; where F_{crit} is the critical value of the central F distribution ($F_{\text{crit}} = F_{\text{numdf}, \text{dmdf}, 0, \alpha}$) under H_0 (H_0 : centrality param = 0), v is the magnitude of the departure from H_0 and ncp is the non-centrality parameter (Stroup).⁹

Phase II

Overall comfort, Comfort at the end of the day, and Dryness at the end of the day

Subjective responses to each primary endpoint will be grouped as: $aval=1$ is a subject responds' 'Excellent' or 'Very Good', $aval=2$ is a subject responds' 'Good' and $aval=3$ if a subject responds' 'Fair' or 'Poor'. $Aval$ will be analyzed separately for each primary endpoint using a generalized linear mixed model with a multinomial distribution and the cumulative logit as the link function. In each model, sequence of lens wear, period and lens type will be included as fixed effects. Site and subject nested within site will be included as a random effect. Errors between measurements within the same subject across study periods will be modeled using an unstructured covariance (UN) structure. Comparisons between O1D and P1 will be carried out using 1-sided 97.5% confidence intervals (CIs) constructed for the odds ratio (O1D over P1). Superiority of O1D relative to P1 will be concluded if the lower limit of the 97.5% CI is above 1.

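### Section 14.5 names a general logit link twice for Phase I, which contradicts its own model equation, the Phase II sizing step and the cumulative logit named for Phase II

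*Combined protocol and SAP*

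**What the plan says.** All of the conflicting text is in protocol Section 14.5, Primary Analysis.

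- **Phase I, main model.** The three-level response (Excellent/Very Good, Good, Fair/Poor) is analysed "using a generalized linear model with a multinomial distribution and the general logit as the link function".
- **Phase I, variance check.** If completion differs enough between sites, a likelihood ratio test is run "using a generalized linear mixed model with a multinomial distribution and the general logit as the link function". This is the second use of the same link name.
- **Phase I, equation.** The first category probability is set equal to the first aval term, the second to the difference between the second and first aval terms, and the third to the remainder. The logit is applied to the aval terms, with a single lens coefficient that carries no category index.
- **Phase I, hypothesis.** One odds ratio per endpoint is tested against 0.67, where "the OR represents the odds of having a more positive experience (Excellent or Very Good) while wearing O1D compared to P1". The bound is obtained "using 10% as non-inferiority margin and assuming a reference proportion of 0.5".
- **Sizing of Phase II.** "The odds ratio and the cumulative log-odds from the model described above for each endpoint will be used to create a new dataset", which is then reanalysed with the same model. Power comes from an F-statistic whose numerator degrees of freedom are left symbolic.
- **Phase II.** The primary endpoints are analysed "using a generalized linear mixed model with a multinomial distribution and the cumulative logit as the link function".

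Nothing in the protocol explains a different link for Phase I, or says how one odds ratio would be taken from a general-logit fit.

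**The concern.** A general logit treats the three categories as unordered and contrasts each non-reference category with a reference. Each endpoint then has two lens odds ratios and a joint lens test on two degrees of freedom. A cumulative logit with a common lens coefficient (proportional odds) has one lens odds ratio and a test on one degree of freedom. An analyst who follows the sentence and an analyst who follows the equation would fit different models to the same data.

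The Phase I model has two jobs: it decides whether non-inferiority is met on each primary endpoint, and it supplies the effect and F-statistic that set the Phase II sample size, up to 300 subjects. If the link is still open when Phase I data arrive, both results depend on an unrecorded choice made at that point.

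**Working it through.** **1. Reproduce the plan's bound.** Inputs from Section 14.5: margin 10 percentage points, reference proportion 0.5.
OR = (0.40/0.60) / (0.50/0.50) = 0.667, which rounds to 0.67. The bound reproduces, as an odds ratio for Excellent/Very Good against all other responses.

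**2. Read the equation.** With p1 = aval1, p2 = aval2 − aval1 and p3 the remainder, aval1 and aval2 must be P(category ≤ 1) and P(category ≤ 2). A logit on these with one shared lens coefficient is a cumulative-logit, proportional-odds model.

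**3. Set the elements side by side.**

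| Element of Section 14.5 | Link it describes |
|---|---|
| Phase I main-model sentence | general |
| Phase I variance-check sentence | general |
| Phase I equation | cumulative |
| Log-odds used for sizing | cumulative |
| Phase II analysis | cumulative |

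The single odds ratio in the hypothesis fits the cumulative model directly, but does not by itself rule out the other (see the objection).

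**4. Size of the difference in odds ratios.** The documents give no P1 response distribution, so the split is an assumption; only the 0.5 in the top category has a basis in the plan. Assume P1 = 50/30/20% and a cumulative OR of 0.67.
- Top category: odds 1 × 0.67 = 0.67, so probability 0.67/1.67 = 0.401.
- Top two categories: odds 4 × 0.67 = 2.68, so probability 2.68/3.68 = 0.728.
- O1D distribution: 40.1 / 32.7 / 27.2%.
- General-logit OR, category 1 vs 3: (0.401/0.272) / (0.50/0.20) = 0.59.
- General-logit OR, category 2 vs 3: (0.327/0.272) / (0.30/0.20) = 0.80.

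For the splits 50/40/10, 50/25/25 and 60/30/10 the pairs are 0.56 and 0.80, 0.60 and 0.80, and 0.59 and 0.84. Including the first split, the ranges are 0.56-0.60 and 0.80-0.84. The two ratios fall on opposite sides of 0.67 each time.

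**5. Size of the difference in the sizing step.** Numerator df: 3 − 1 = 2 under the general logit, 1 under the equation. Noncentrality needed for 80% power (noncentral chi-square):

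| Alpha | 1 df | 2 df | Ratio |
|---|---|---|---|
| 0.05 | 7.85 | 9.63 | 1.23 |
| 0.0167 (Section 14.4) | 10.47 | 12.56 | 1.20 |

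At the noncentrality that gives 80% power on 1 df, the 2-df test has about 71%. With a noncentral F and an assumed 106 denominator df, the ratios are 1.24 and 1.21.

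**6. Size at the interim decision.** In 500 simulated datasets (true OR 1, P1 50/30/20%, 60 responses per lens, responses taken as independent), the one-sided 97.5% lower limit exceeded 0.67 in about 10% of datasets using the general-logit category 1 vs 3 ratio, and in about 20% using the cumulative logit. Independence is a simplification for crossover data, so only the contrast between the two is informative.

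**The case against.** The strongest reply is that the plan writes its likelihood out in full. Anyone who programs that likelihood gets one lens odds ratio and the test as stated. The sizing text and the Phase II link agree with the equation; only a link label, used twice in one paragraph, is out of line. This largely stands, and it makes a naming error the most likely explanation. It does not remove the contradiction, because the sentence that names the link is itself an instruction to the programmer.

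A reader might infer that the stated interim model cannot produce the stated test. The documents do not support that. The equation already produces it. Even under a general logit, a top-category-versus-rest odds ratio could be derived from the fitted probabilities; in the illustration, (0.401/0.599)/(0.5/0.5) = 0.67. What is missing is any instruction to do so. So the single odds ratio does not strictly demand a cumulative logit, whereas the equation and the cumulative log-odds do.

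A reader might also infer that Phase II will be mis-sized by about a fifth. That would follow only if the general logit were fitted against the plan's own equation, and the plan never states a 2-df test.

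Two further defences carry less weight. Section 14.2 says Phase I was not powered for non-inferiority, yet Section 14.5 makes sizing conditional on showing it. Section 14.1 defers detail to a stand-alone SAP, but requires that SAP only before database lock and does not tie it to the interim analysis.

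**Conclusion.** The contradiction is real and lies wholly within Section 14.5: the link named twice for Phase I is not the link of the Phase I equation, the sizing inputs or the Phase II analysis. It affects the interim non-inferiority decision and the Phase II sample size. It does not reach the Phase II analysis, which names the cumulative logit.

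The consequence is conditional. If the named link were fitted, each endpoint would have two lens odds ratios and no rule for choosing between them, 0.59 and 0.80 in the illustration, together with a lens test needing about 20-23% more noncentrality for 80% power. The odds ratios rest on assumed P1 splits and a cumulative odds ratio at the bound. The noncentrality figures rest only on 2 against 1 df and the two alpha levels. These figures measure what the ambiguity could cost; they do not predict an error in this trial.

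**What to change.** Before the interim analysis, replace general logit with cumulative logit in both Phase I sentences of Section 14.5 (main model and variance check). They then match the equation, the hypothesis, the sizing step and Phase II. The sponsor should confirm that this was the intent. If a general logit was meant, the larger task is to rewrite the equation, the hypothesis and the sizing text, and to state which odds ratio is tested.

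The cost is two wording edits, with no change to data collection or design. The absence of a subject effect from the Phase I model is a separate issue and should be raised on its own; this edit does not address it.

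### The interim model that sizes Phase II ignores the pairing of each subject's two responses, so both the non-inferiority interval and the Phase II sample size use the wrong variance

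*Combined protocol and SAP*

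**What the plan says.** **Phase I model (14.5).** "In each model, sequence of lens wear, period, lens type and site id will be included as fixed effects". The printed equation has the same four terms and no subject effect, and no clustered variance is named. A mixed model appears in Phase I only for a conditional test of variance homogeneity when completion differs between sites by more than 30%.

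**Gate (14.5).** "If non-inferiority is demonstrated for the primary endpoints, the sample size required to test superiority for each primary endpoint will be estimated". Non-inferiority needs a lower 97.5% bound above an odds ratio of 0.67.

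**Sizing (14.2 and 14.5).** Power is to be "derived from the non-centrality parameter calculated from the observed F-statistic from the generalized linear model described in Section 14.5 for Phase I". What is carried forward is "The odds ratio and the cumulative log-odds from the model described above". Then: "This new dataset will then be analyzed using the same model". Section 14.5 computes power endpoint by endpoint, whereas 14.2 and 14.8 ask for at least 80% power for all three primary hypotheses.

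**Cap (14.2).** "If the sample size calculation for Phase II exceeds 300 then the Sponsor reserves the right to terminate the study". Section 14.8 adds that the study may stop if the required size is too large.

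**Phase II model (14.5).** "Site and subject nested within site will be included as a random effect", together with an unstructured within-subject covariance.

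**Completeness.** Section 14.1 leaves further detail to a separate SAP, but 14.2 says: "Complete details of the sample size calculation for Phase II are described in Section 14.5".

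**The concern.** Section 4.2 justifies the crossover because each subject serves as his or her own control. That gain comes from within-subject correlation. The model behind the gate and the sizing treats the 120 responses of 60 completers as 120 independent people. With positive correlation, this overstates the variance of the lens contrast by roughly 1/(1−correlation).

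Two decisions use that variance: whether Phase II is sized at all, and whether its size fits under 300. If the variance is too large, a promising comparison could be stopped for no good reason. The Phase II analysis would then have used a different, more efficient model from the one that stopped it.

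**Working it through.** **1. The plan's own figures.** Margin: (0.4/0.6)/(0.5/0.5) = 0.667, which reproduces 0.67. Alpha: 0.05/3 = 1.67%, which reproduces 14.4. The plan states no Phase II N, so there is none to reproduce.

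**2. What enters the sizing.** Only the odds ratio (OR) and cut-points are carried forward, and the same fixed-effects model is refitted. No within-subject correlation can enter.

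**3. Assumed inputs.** The documents give no effect size, response split or correlation; 4.2 says there are no historical data for P1. Assumed: P1 split 50/30/20 over the three grouped categories, and within-subject response correlation 0 to 0.50. I used the cumulative-logit form. Section 14.5 names a general logit for Phase I, but its equation and the quantities carried forward are cumulative.

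**4. Interim standard error of the log OR.** Simulation with n=60, 10 sites of 6 and true OR 1:

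| Correlation | 0 | 0.20 | 0.35 | 0.50 |
|---|---|---|---|---|
| Model SE | 0.356 | 0.358 | 0.358 | 0.359 |
| True SD | 0.383 | 0.351 | 0.322 | 0.284 |
| Ratio − 1 | −7% | +2% | +11% | +26% |

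The smallest passing OR is 0.67·exp(1.96·SE). With the model SE of 0.358 this is 1.35. With the true SD it is 1.42, 1.33, 1.26 and 1.17 across the four columns. At a true OR of 0.67, the per-endpoint pass rate is 2.6/1.5/0.8/0.4% as written, against a nominal 2.5%.

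**5. N per endpoint at a fixed OR of 1.5, 80% power.** N = (z(1−α)+0.842)²·V/(log 1.5)². The independence model gives V = 7.52 per subject, and (log 1.5)² = 0.1644.
- One-sided 1.67%: (2.128+0.842)²·7.52/0.1644 ≈ 404.
- One-sided 2.5%: (1.960+0.842)²·7.52/0.1644 ≈ 359.
- Variance clustered on subject, correlation 0.20/0.35/0.50: 327/269/212 at 1.67% and 291/239/188 at 2.5%. The variance ratios are 1.24/1.50/1.91, close to 1/(1−correlation) = 1.25/1.54/2.00.

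**6. The joint target.** Assume equal ORs, normal estimates, and correlation between the three endpoint estimates of 0.55–0.68 (the range seen in the simulations, where the endpoints' latent correlation was set at 0.8). If each endpoint has 80% power, joint power is only 62–65%. Joint power of 80% needs about 90–91% per endpoint. N is then multiplied by 1.30–1.35 at 1.67%, or 1.32–1.37 at 2.5%.

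| Correlation | 0.20 | 0.35 | 0.50 |
|---|---|---|---|
| Needed, 1.67% | 425–441 | 350–362 | 276–286 |
| Plan, 1.67% | 404 | 404 | 404 |
| Needed, 2.5% | 384–399 | 315–327 | 248–258 |
| Plan, 2.5% | 359 | 359 | 359 |

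At 1.67% the plan's 404 is too small at 0.20 (joint power 75–77%). At 0.35 it is 12–15% too large (404/362 to 404/350), with both numbers above 300. It is needlessly above 300 only at about 0.50.

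**7. Go/no-go.** This is the share of runs that pass the gate on all three endpoints and have N ≤ 300, at true OR 1.5 and correlation 0/0.20/0.35/0.50. N is the largest of the three per-endpoint values at 1.67%; the gate uses the 97.5% bound.
- As written: 25.5/25.4/24.5/23.1%.
- With clustered variance only: 23.0/27.1/30.6/36.2%.

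Median N in those runs is 166/172/181/197 as written and 176/169/163/157 with clustered variance. A single endpoint needs 404/327/269/212. The shortfall arises because N is computed from the observed OR after the gate has selected large ones. These runs do not use the joint target, which would raise N.

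**The case against.** **The correlation is unknown and the sign depends on it.** This stands. At zero correlation the clustered gate is stricter: three-endpoint pass at OR 1.5 falls from 42.5% to 35.6%. At 0.20 the two are nearly equal. The value 0.35 is an assumption on the response scale, not a threshold.

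**The inflated variance offsets the per-endpoint power calculation.** This stands too, and it limits the claim. A reader might set 404 against 269 at correlation 0.35 and infer that the cap is crossed needlessly there. Sections 14.2 and 14.8 do not support that, because their target is power for all three hypotheses, and the N needed on that target is itself above 300.

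**Phase II might be thought oversized overall.** The documents do not support that inference either. Sizing on an observed OR from about 60 subjects after a gate pulls N down, and correcting the variance alone lowers it further at positive correlation.

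**Stopping is discretionary, and no wrong claim results.** Correct. The sponsor only reserves the right to stop, the cap rests on resources and timing, and Phase II superiority is tested with a model that includes subject. The error cannot by itself produce a false superiority claim.

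**The separate SAP could settle it.** This fails: 14.2 says that 14.5 already holds the full sizing method, and that method is explicit.

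**Conclusion.** The mismatch is in the text: a stated rule treats paired responses as independent for the gate and the sizing, and a different model analyses Phase II. The text finding is firm; the size of the harm rests on assumed correlations, ORs and splits.

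- **Interim interval:** about 7% too narrow at zero correlation, about right near 0.20, and 11% and 26% too wide at 0.35 and 0.50. From about 0.35 upward the gate is too strict. The gate was simulated only with the 97.5% bound, not at 1.67%.
- **Sizing:** per-endpoint N is overstated by about 1/(1−correlation). Against the joint target at OR 1.5 and 1.67%, the plan's N is too low at 0.20, modestly high at 0.35, and needlessly over the cap only at about 0.50.
- **Go/no-go:** discretionary, with a direction that depends on the correlation.

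This is worth fixing before the interim analysis, at the lower end of that category.

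**What to change.** 1. **Interim interval.** Use the cumulative-logit model of the printed equation, with variance clustered on subject (GEE or robust) and a small-sample correction. This keeps the OR on the marginal scale from which 0.67 was derived. Moving the gate to the Phase II mixed model while keeping 0.67 would barely change pass rates, because that model's OR is subject-specific.
2. **Sizing model.** Generate and analyse the sizing dataset with the Phase II within-subject structure. Carry in the OR, cut-points and subject variance which that model estimates from Phase I.
3. **Power target.** Size for 80% joint power on all three primary endpoints, not 80% on each.
4. **Alpha.** Reconcile 1.67% in 14.4 with the 97.5% bounds in 14.5. Use the agreed level at the gate, in the sizing and in the Phase II decision.
5. **Range.** Report N over lower ORs and lower subject variances. About 60 subjects estimate both poorly: for a true subject SD of 1.00, the 10th to 90th percentile of the estimate was 0.27–1.69.

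Make steps 2, 3 and 5 together. Step 2 alone can lower an N already selected downward.

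**Cost:** protocol and SAP wording and more programming before the interim analysis. Phase I needs no extra subjects; the joint target can raise the Phase II N. The subject variance will be imprecise, and the gate becomes somewhat stricter if the true correlation is near zero.
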